10.12. Approximate Blood Volume

During the study, blood will be drawn for various analytes and panels, including chemistry, hematology, coagulation, PK, PD (cardiac markers, inflammatory markers), and serotonin concentration assessments. The approximate amount of blood to be drawn over the course of the study for each subject is expected to be 175 mL.

10.13. Procedures for Overdose

Overdose is not expected as study treatment will be administered in a highly controlled environment by qualified designees at the study centers. The Sponsor does not recommend

specific treatment for an overdose; there is no known antidote to temanogrel. After an overdose or suspected overdose, subjects should be monitored for adverse events.

If a subject receives a dose in excess of the instructed dose (eg, due to pharmacy error) and if symptoms are present, the Investigator or designee should contact the Medical Monitor immediately. In the absence of associated adverse events as assessed per the clinical judgement of the Investigator, no further action is required.

11. PLANNED STATISTICAL METHODS

11.1. General Considerations

Details regarding the statistical analyses will be provided in a Statistical Analysis Plan (SAP), which will be finalized prior to study database lock (unblinding).

Continuous variables will be summarized using the number of observations (n), mean, standard deviation (SD), median, minimum, and maximum. Categorical variables will be summarized using frequency counts and percentages.

Unless otherwise specified, continuous endpoints will be analyzed using analysis of covariance (ANCOVA) with a model that includes treatment group and randomization stratification factor as factors and Baseline IMR value and Baseline value as covariates. Least square means, standard errors (SEs), and 95% confidence intervals (CIs) for the treatments and their difference will be presented together with their p-value.

Proportion-based endpoints will be analyzed by either the Cochran-Mantel-Haenszel method adjusting for randomization stratification factor. The number and percentage of subjects achieving the goal and the difference in proportion between treatment groups achieving the goal, along with p-value and the 95% CIs will be reported. The odds ratio relative to placebo and percentage of difference from placebo will be presented together with corresponding 95% CIs and the p-value.

Pairwise comparisons of each temanogrel treatment group compared to placebo will be conducted. In addition, analyses of the pooled temanogrel treatment groups compared to placebo will be conducted.

Where statistical assumptions (eg, normality, proportional odds) are not met, alternative approaches will be evaluated (eg, non-parametric analysis, log transformation).

Efficacy data will be analyzed by randomized treatment, while safety data will be analyzed by actual treatment received.

All secondary and exploratory analyses will be interpreted in an exploratory manner.

11.2. Determination of Sample Size

This study is planned to randomize, treat, and complete safety, tolerability, PK, and PD assessments in approximately 99 subjects (12 in Stage A, 87 in Stage B).

It is assumed that the primary endpoint, which is the change from Baseline in IMR measured immediately after PCI, is normally distributed with a mean of 6 and SD of 3.5. Assuming a 1:1:1 randomization, 90 evaluable subjects (30 subjects in each of the 2 temanogrel treatment groups and placebo) is sufficient to achieve at least 90% power to detect a treatment effect of 3 (a clinically significant reduction of 50% from placebo) between each of the temanogrel treatment groups and placebo by a 2-sample t-test using a 2-sided significance level of 0.05.

The primary endpoint analysis will be based on pooled data from subjects in Stage A and Stage B.

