Stage A is an ascending single-dose study planned to consist of 2 cohorts. After treatment of each cohort in Stage A, a safety/tolerability assessment will be conducted by the Data and Safety Monitoring Board (DSMB). Following the safety review of the first cohort in Stage A, the DSMB will recommend whether dose escalation to the next planned dose level in Stage A should occur; the DSMB may also recommend evaluation of an alternative dose in the second cohort in Stage A. Following the safety review of the second cohort in Stage A, the DSMB will recommend whether progression to Stage B should occur; the DSMB may also recommend evaluation of an alternative dose in an additional third dose cohort in Stage A prior to progression to Stage B. After conduct of the final cohort and safety review of Stage A, Stage B may begin. Stage B is a parallel-treatment group study planned to consist of a placebo group and 2 active treatment groups (temanogrel doses selected based on safety and tolerability data in Stage A). In Stage B, enrollment will consist of no more than 25% elective PCI subjects and randomization will be stratified subject type (elective PCI or PCI for non-ST-elevation myocardial infarction [NSTEMI]/unstable angina [UA]).

Subjects should be treated with aspirin and an oral P2Y₁₂ inhibitor (ie, dual antiplatelet therapy [DAPT]) per site standard of care; however, subjects in Stage A may only be treated with clopidogrel as the P2Y₁₂ inhibitor DAPT component and may not be treated with prasugrel or ticagrelor until after the subject has completed study participation.

Number of subjects (planned):

Approximately 99 subjects are planned to be enrolled in this study. In Stage A, 2 cohorts are planned and approximately 6 subjects will be enrolled in each cohort (4 temanogrel:2 placebo per cohort). One additional cohort (4 temanogrel:2 placebo per cohort) may be enrolled to explore an additional dose if deemed appropriate based upon data reviews of prior cohorts. In Stage B, approximately 87 subjects are planned to be enrolled (29 subjects in each of the 2 temanogrel treatment groups and the placebo group).

Eligibility criteria:

Inclusion criteria:

Subjects must meet ALL of the following inclusion criteria to be eligible for enrollment into the study:

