Temanogrel is an IV formulation containing active pharmaceutical ingredient provided as 25 mg/mL strength. Temanogrel IV solution will be prepared by blinded study staff. Subjects assigned to active treatment will receive 1 single dose in total as a 5 mL IV bolus administered in the forearm over duration of at least 5 minutes.

The temanogrel dose to be administered to Cohort 1 of Stage A will be 20 mg. The dose administered in Cohort 2 is planned to be 40 mg. One additional dose cohort may be explored in Stage A if deemed appropriate based upon data reviews of prior cohorts. Selected doses from Stage A are planned to be investigated in Stage B of the study. Planned doses in Stage A and Stage B may be adjusted depending on the safety and tolerability results of previous cohort(s). Doses in this study will not exceed 40 mg.

Duration of treatment:

Subjects will receive a single IV dose of study treatment on Day 1 of the study.

Reference therapy, dose, and mode of administration:

Placebo will be packaged to match temanogrel. Volume and mode of administration of placebo will match that of temanogrel to maintain the blind.

Endpoints:

Primary endpoint:

- Change in IMR from Baseline to Post-PCI

Secondary endpoints:

- Change from Baseline to Post-PCI for the following assessments:
 - Coronary physiology indices (coronary flow reserve [CFR], fractional flow reserve [FFR])
 - Angiographic measures (corrected thrombolysis in myocardial infarction frame count [cTFC], TFG, thrombolysis in myocardial infarction myocardial perfusion grade [TMPG])
 - Myocardial injury markers (creatine kinase [CK], creatine kinase-myocardial band [CK-MB], cTn)

Note: Post-PCI measure for CK, CK-MB, and cTn, is collected 4 to 6 hours after completion of the PCI procedure and not immediately after completion of the procedure.

- The incidence of procedural myocardial injury defined as elevation of cTn values > 99th percentile upper reference limit (URL) in subjects with normal Baseline values (\leq 99th percentile URL) or elevation of cTn by > 20% of the Baseline value in subjects with elevated cTn levels (> 99th percentile URL)
- Concentration of temanogrel and active metabolites AR295980 and AR295981 prior to PCI and at selected post-PCI timepoints until discharge
- Safety and tolerability of temanogrel

Pharmacokinetic assessments:

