6.3. Dosage and Administration

The study treatment will arrive at the site blinded and will be administered in a blinded fashion to the subjects. A delegated study staff will be responsible for providing temanogrel or placebo to study personnel for administration as per the randomization scheme. For each subject, study treatment preparation will occur after the subject has been randomized. All doses will be diluted to a final volume of 25 mL. Each subject will be dosed intravenously with 5 mL of this prepared volume. Dilution instructions will be provided in a separate pharmacy manual.

An aliquot of the prepared dilution (3 mL) will be collected and appropriately stored as described in the Pharmacy Manual. Aliquots may be analyzed to confirm dose concentration.

Study treatment will be administered intravenously. All enrolled subjects will receive a single IV dose of study treatment. Temanogrel dose to be administered to Cohort 1 of Stage A will be a 20 mg IV bolus (to be administered in the forearm over a period of not less than 5 minutes). Planned doses administered to subsequent cohort(s) in Stage A and selected doses for Stage B may be adjusted depending on the safety and tolerability data of previously treated subjects. Doses in this study will not exceed 40 mg. Placebo administration duration, administration location, and volume will match that of temanogrel. Hour 0 will correspond to the start of the IV bolus administration.

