6.4. Method of Assigning Subjects to Treatment

Each subject will be assigned a unique identification number upon Screening. Eligible subjects will be centrally randomized into the study using an interactive response technology (IRT) system. Subjects who complete the study Screening assessments and meet all the eligibility criteria will be assigned a unique randomization identification number at the time of study treatment administration, different from the screening number, and will receive the corresponding product according to a randomization scheme.

Subject identification numbers will be 12 characters in length, including dashes, 202-CCSS-XXX. The first 3 digits represent the study number, the 4 digits following the first dash represent the combination of country code (CC) and the site number (SS), and the last 3 digits represent the subject number. Subject numbers will be assigned strictly sequentially at every site as subjects become eligible for enrollment, starting from 001.

In Stage A, eligible subjects will be randomly assigned to study treatment in a 2:1 ratio (temanogrel:placebo). In Stage B, eligible subjects will be randomly assigned to study treatment in a 1:1:1 ratio (20 mg:40 mg:placebo), stratified by subject type (elective PCI or PCI for NSTEMI/UA).

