11.5. Efficacy Analyses

The primary and secondary endpoints will be analyzed using the Full Analysis Set (FAS). Other important statistical considerations such as sensitivity analyses and subgroup analyses will be described in the SAP.

The primary endpoint of the study is the change from Baseline in IMR measured immediately after PCI. The primary PD analysis will be analyzed using ANCOVA with a model that includes treatment group and randomization stratification factor as factors and Baseline IMR as a covariate. Least square means, standard errors (SEs), and 95% CIs for the treatments and their difference will be presented together with their p-values.

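### The primary ANCOVA pools two separately randomised stages without a stage term; adding one costs a single degree of freedom and recovers precision if the stages differ

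*Combined protocol and SAP*

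**What the plan says.** Section 11.2 (and the synopsis) pools the stages for the primary endpoint: "The primary endpoint analysis will be based on pooled data from subjects in Stage A and Stage B". Section 11.5 gives the primary model as a "model that includes treatment group and randomization stratification factor as factors and Baseline IMR as a covariate". Neither stage nor cohort appears in it, and no other section adds either.

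The stages are randomised differently. Section 6.4 gives Stage A a 2:1 allocation and mentions no stratification. For Stage B it says: "In Stage B, eligible subjects will be randomly assigned to study treatment in a 1:1:1 ratio (20 mg:40 mg:placebo), stratified by subject type". The stratification factor is therefore subject type, stated for Stage B only, and it does not carry stage.

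Stage A consists of sequential cohorts of about six subjects, four on temanogrel and two on placebo. Section 6.3 says: "Temanogrel dose to be administered to Cohort 1 of Stage A will be a 20 mg IV bolus". The synopsis adds: "The dose administered in Cohort 2 is planned to be 40 mg". It also says: "One additional cohort (4 temanogrel:2 placebo per cohort) may be enrolled". Stage B has 29 subjects per group.

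Two further differences are written into the protocol. Clopidogrel is the only P2Y12 inhibitor allowed in Stage A, while Stage B allows any (Section 6.7.1). Elective PCI is capped at 25% in Stage B only (Section 3.1).

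**The concern.** When separate randomisations are combined, the usual analysis includes a term for the randomisation each subject came from. Here the change in IMR could differ between stages because of background platelet inhibition or calendar time. Section 3.2 itself links serotonin release to platelet activation and plans to measure inhibition from background therapy. The elective cap is not part of the concern, because subject type is already in the model.

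A stage difference not explained by subject type or Baseline IMR would sit in the residual. The standard error would then be too large, the interval wider than necessary, and the test conservative. If the arms had unequal Stage A shares, the treatment difference would also be biased.

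**Working it through.** **Inputs.** From Sections 11.2 and 6.4 and the synopsis: SD 3.5, effect 3, two-sided 0.05, 12 subjects in Stage A (4 per arm over two cohorts) and 87 in Stage B (29 per arm), so 33 per arm and 99 in total. The Stage A minus Stage B shift D, after subject type and Baseline IMR, is an assumption: 0, 1, 3 or 5 IMR units.

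**The plan's own figure.** For 30 per group the noncentrality is 3 / (3.5 × √(2/30)) = 3.32, and the noncentral-t power is 90.4%. With 29 per group it is 89.4%. The stated 30 per group for at least 90% power reproduces.

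**Cost of the term.** The Section 11.5 model has five parameters (intercept, two for treatment, one for stratum, one for Baseline IMR), so residual df = 99 − 5 = 94, or 93 with stage. The critical t moves from 1.98552 to 1.98580. With D = 0 the 95% half-width, t × 3.5 × √(2/33), moves from 1.7108 to 1.7110.

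**Effect of leaving it out.** Stage is balanced across arms (4 of 33 in each), so the expected treatment difference does not change. The expected residual variance becomes

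3.5² + (12 × 87/99) × D² / 94 = 12.25 + 0.1122 × D².

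- D = 3: 13.26, residual SD 3.641, half-width 1.780.
- D = 5: 15.06, residual SD 3.880, half-width 1.897.
- With the term: half-width 1.711 for any D.

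The stage term gives the shorter interval once D exceeds about 0.17.

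**Simulation of the ANCOVA.** Settings: planned layout; 7 of 29 elective per arm in Stage B and 25% drawn in Stage A; no effect of subject type or Baseline IMR; within-stage SD 3.5; power averaged over both dose contrasts, 200,000 trials per scenario (100,000 for error).

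| D | Power, no term | Error, no term | Half-width, no term |
|---|---|---|---|
| 0 | 0.929 | 0.050 | 1.72 |
| 1 | 0.927 | 0.049 | 1.72 |
| 3 | 0.917 | 0.042 | 1.79 |
| 5 | 0.895 | 0.032 | 1.90 |

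With the stage term, power is 0.928 to 0.930, error 0.048 to 0.050 and half-width 1.72 for every D.

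**If 3.5 is already the pooled SD.** The within-stage SD is then √(3.5² − D² × (12/99) × (87/99)) = 3.485, 3.360 and 3.096 for D = 1, 3 and 5. Power without the term is 0.929, 0.936 and 0.950. With it, power is 0.930, 0.945 and 0.972.

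**Optional third cohort, with Stage B testing 20 and 40 mg.** Placebo then has 6 of 35 subjects from Stage A, against 4 of 33 per dose. The bias has size (6/35 − 4/33) × D = 0.050 × D, that is 0.05, 0.15 and 0.25 for D = 1, 3 and 5. Simulation gives about 0 with the stage term. The pooled temanogrel comparison, including the third dose, stays balanced (12/70 = 6/35).

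**Difference between Cohorts 1 and 2.** All Stage A subjects on 20 mg are in Cohort 1 and all on 40 mg in Cohort 2, with placebo split two and two. A Cohort 2 minus Cohort 1 difference δ gives a bias of −(2/33)δ for 20 mg and +(2/33)δ for 40 mg. For δ = 3 that is 0.18 in size. A stage term leaves it in place. A term with levels Cohort 1, Cohort 2 and Stage B removes it, at a cost of two df (94 to 92), a rise in standard error from 0.862 to 0.871, and power of 0.924 when there is no shift.

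**The case against.** The strongest reply is that nothing in the plan is wrong. Under the planned layout the model is unbiased and slightly conservative, which is acceptable in a study that Section 11.8 describes as exploratory. The shift is an assumption. At D = 1 almost nothing is lost, and power falls below 90% only at D = 5, which is 1.4 SD and five-sixths of the assumed mean change of 6. If 3.5 is the pooled SD, power never falls below 0.929. Stage B also allows clopidogrel, so background therapy does not fully separate the stages, and Section 11.7 already lists P2Y12 subgroups. The only bias in the planned layout, between cohorts, survives a stage term.

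All of that stands as a limit on size. It does not favour leaving the term out, because including it costs nothing measurable. Subgroup analyses do not adjust the primary model.

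Two further points concern what can be known. The SAP stayed at draft v0.3 and is not available, and the protocol does not say how Stage A subjects are coded on the stratification factor. Had Stage A been coded as its own level, stage would already be in the model. Section 11.5 does not say so, and that silence also needs correcting. Finally, enrolment was terminated and the contents of the final report list summaries and listings of coronary physiology but no ANCOVA. The practical effect on this trial is therefore limited, though what the written plan specifies is unchanged.

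**Conclusion.** The concern holds and is minor. As written, the primary model combines two separately randomised stages with no term for stage. With the planned 4 of 33 per arm the consequence is lost precision, not bias: for an assumed residual shift of 3 IMR units and a within-stage SD of 3.5, about one percentage point of power and an interval about 4% wider (1.79 against 1.72). The loss is negligible for a shift of 1. A bias of 0.050 times the shift arises only if the third cohort runs and Stage B tests the doses of Cohorts 1 and 2. The size of any real shift is unknown. The finding is against the protocol's model, since the draft SAP cannot be checked.

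**What to change.** In Section 11.5 and the synopsis, add stage (A or B) as a factor in the primary ANCOVA, and do the same in the secondary continuous ANCOVAs if they are pooled. State that the stratum for Stage A subjects is their recorded subject type (elective PCI or NSTEMI/UA).

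As an optional sensitivity analysis, replace stage with randomisation unit: Cohort 1, Cohort 2, Stage B, and Cohort 3 if it runs. This also removes the between-cohort bias. It suits a sensitivity analysis better than the primary model because it lowers power by about half a percentage point.

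The primary change is wording only. It needs no extra patients, takes residual df from 94 to 93, and leaves power at 0.929 when the stages do not differ.

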11.3. Analysis Sets

For purposes of analysis, analysis sets are defined in [Table 4](#).

Table 4: Analysis Sets

Analysis Set	Description
Full Analysis Set (FAS)	The FAS will include all randomized subjects, irrespective of whether they received any study treatment.
Modified Full Analysis Set (mFAS)	The mFAS will include all subjects in the FAS who receive any study treatment and have at least a Baseline and Post-PCI IMR measurement.
Per Protocol Set	The Per Protocol Set will include all subjects in the FAS who receive the full dose of study treatment, have a Baseline and Post-PCI IMR measurement, and are without major protocol violations that might affect the evaluation of the effect of study treatment on the primary endpoint, which will be defined in the SAP.
Pharmacokinetic Set	The Pharmacokinetic Set will include all subjects in the Safety Set with at least 1 postdose PK measurement.
Safety Set	The Safety Set will include all subjects in the FAS who receive any study treatment.

11.4. Missing Data

Due to the trial design and short study duration, minimal missing data is expected. As a result, no algorithm for missing data imputation will be employed.

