8.2. Discontinuation from the Study

Subjects may discontinue/be discontinued from the study at any time for any of the following reasons:

- Adverse event
- Death
- Pregnancy (Section 10.8.6)
- Protocol deviation
- Investigator decision
- Withdrawal by subject
- Study termination by Sponsor
- Other

A subject may elect to discontinue study participation at any time for any reason without prejudice to their future medical care by the physician or at the institution.

Subjects who are randomized but not subsequently dosed and subjects who discontinue study participation will be considered Early Termination subjects. Should a subject become unwilling or unable to complete the remaining scheduled PK/PD and safety assessments (individual missing data points do not count as early discontinuation), the Follow-Up phone contact should be performed as described in protocol Section 9.4 (Early Termination).

If a subject withdraws consent for any further evaluation, no further evaluation will be performed, no additional data should be collected, and samples must be destroyed. The Sponsor may retain and continue to use any data collected before such withdrawal of consent. The Investigator should make a reasonable attempt to document the specific reason why consent was withdrawn.

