9.4. Early Termination

Subjects who are randomized but not subsequently dosed and subjects who discontinue study participation will be considered Early Termination subjects. Should a subject become unwilling or unable to complete the remaining scheduled PK/PD and safety assessments (individual missing data points do not count as early discontinuation), the Follow-Up phone call should be performed for subjects who received a dose of randomized study treatment. Site staff should work with subjects who withdraw early to obtain as much follow-up data as possible.

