10.4. Pharmacodynamic Assessments

10.4.1. Coronary Physiology Indices

Assessment of coronary physiology indices will be performed on all randomized subjects and will be used to characterize the PD effects of temanogrel. Indices of coronary physiology to be assessed in this study include IMR (Section [10.4.1.1](#)), coronary flow reserve (CFR) (Section [10.4.1.2](#)), and fractional flow reserve (FFR) (Section [10.4.1.3](#)). Coronary physiology indices will be assessed and analyzed as previously described ([Fearon 2000](#)) using the

Coroventis CoroFlow™ Cardiovascular System, v3.0 or later, and details on the applicable methods can be found in a separate operation manual. The coronary physiology indices will be assessed at three timepoints: Baseline values will be assessed before study treatment administration (after randomization at Baseline, unless already assessed at Check-in for confirmation of suitability for PCI per institutional standards; in that case these values can be used as Baseline values), Pre-PCI values after completion of study treatment administration, but before the PCI procedure, and Post-PCI values within 15 minutes of completion of the PCI procedure. Planned timepoints for assessment of coronary physiology indices are provided in the Schedule of Assessments ([Appendix 1](#)). Additional details regarding the procedures for collection and transfer of coronary physiology indices data will be provided in a separate operation manual.

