10.9. Order of Events and Priority for Timed Assessments

Every effort should be made to perform procedures as closely as possible to the scheduled times indicated in the Schedule of Assessments ([Appendix 1](#)).

On Day 1, the timing of events should first be determined by subject safety requirements and then by the scheduled times and sequential order of events as described in this protocol, giving consideration to appropriate posture conditions, practical restrictions, and the other procedures scheduled to be performed at the same timepoint. The preferred order of events in the Peri-PCI period is as follows:

1. Diagnostic angiography including confirmation of lesion-related eligibility (not required if a diagnostic angiography obtained within 60 days prior to Day 1 confirms lesion characteristics)
2. Randomization
3. Baseline peripheral blood draw
4. Baseline target vessel angiographic measures (not required to be repeated if completed during diagnostic angiography at Check-in; in cases when diagnostic angiography is not performed at Check-in, lesion and vessel characteristics should be assessed as part of Baseline target vessel angiographic measures assessment prior to administration of study treatment)
5. Baseline coronary physiology indices (IMR, CFR, FFR; not required to be repeated if completed at Check-in for confirmation of suitability for PCI per institutional standards)
6. Treatment administration
7. Post-treatment / pre-PCI peripheral blood draw (collected 0-2 minutes after the end of the IV administration of randomized study treatment)
8. Post-treatment / pre-PCI coronary physiology indices (IMR, CFR, FFR)
9. PCI with predilation (if applicable) and stent deployment
10. Post-PCI (within 15 minutes of the completion of the PCI procedure) coronary artery (coronary ostium and coronary artery distal to the lesion) blood sampling

11. Post-PCI (within 15 minutes of the completion of the PCI procedure) coronary physiology indices (IMR, CFR, FFR)
12. Post-PCI (within 15 minutes of the completion of the PCI procedure) target vessel angiographic measures
13. Post-PCI (within 15 minutes of the completion of the PCI procedure) peripheral blood draw

Specific timing of the study activities listed above is not critical (unless specified) as long as activities are completed in the order specified.

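### Does an all-randomised primary ANCOVA with no imputation leave the IMR comparison open to bias that the plan must address?

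*Combined protocol and SAP*

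**What the plan says.** Table 4 in Section 11.3 defines the analysis set broadly: "The FAS will include all randomized subjects, irrespective of whether they received any study treatment". Section 11.5 assigns the primary and secondary endpoints to that set. The primary model is an ANCOVA of change in IMR from Baseline to Post-PCI, with treatment and the randomisation stratum as factors and Baseline IMR as covariate. Section 11.4 expects minimal missing data because of the design and short duration, and concludes: "As a result, no algorithm for missing data imputation will be employed". Section 11.5 also says: "Other important statistical considerations such as sensitivity analyses and subgroup analyses will be described in the SAP".

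Table 4 defines two further sets that require both IMR values, the modified FAS (mFAS) and the Per Protocol Set. The protocol assigns no analysis to either. Section 10.4.1 plans the measurement for everyone: "Assessment of coronary physiology indices will be performed on all randomized subjects". Sections 8.2 and 9.4 recognise subjects who are randomised but not dosed, and say that "individual missing data points do not count as early discontinuation".

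**The concern.** A result labelled as covering all randomised subjects would in fact come from those with both IMR values. It would be nearly the mFAS, differing only by any undosed subjects who have both measurements. The validity of the comparison then rests on missingness being unrelated to the unseen outcome, given arm, stratum and Baseline IMR, and the protocol never says so.

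The worry is a patient with poor flow or instability after stenting who misses the Post-PCI measurement. Section 10.9 says that on Day 1 "the timing of events should first be determined by subject safety requirements", which makes such a loss conceivable. An isolated missing IMR does not make the subject an Early Termination case, so that route records no reason for it. Sensitivity analyses were left to the SAP, and the Note to File of 07 October 2022 says the SAP will stay in draft (v0.3). With about 33 subjects per arm, a few outcome-related losses concentrated in one arm could hide an effect (if on placebo) or exaggerate one (if on temanogrel).

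**Working it through.** **Inputs.** From Section 11.2: mean change 6 on placebo, difference 3, SD 3.5, two-sided 0.05, two-sample t-test, 30 evaluable per group, about 99 subjects planned. From the Synopsis: Stage A has two cohorts of 4 temanogrel and 2 placebo, and Stage B has 29 per group. Pooled, that is 4 + 29 = 33 per group (4 at each dose; 2 + 2 = 4 placebo). No missing-IMR rate is given, so every loss pattern below is an assumption.

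**1. The plan's own figure.** Noncentral-t power with noncentrality 3 / (3.5 × √(2/n)):
- n = 30: power 0.904, so the stated figure of at least 90% reproduces.
- n = 33: power 0.929.

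Planned 99 less evaluable 90 leaves 9 subjects, and 9/99 = 9.1%. Random loss of that size costs power only (0.929 to 0.904) and no bias.

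**2. Worst-case selection.** Suppose the k largest changes among 33 are lost in one arm. The observed mean of that arm falls by 3.5 × (sum of the k largest expected normal scores) / (33 − k).
- k = 1: 3.5 × 2.08 / 32 = 0.23.
- k = 3: 3.5 × 5.16 / 30 = 0.60.

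Simulated t-tests, unadjusted for baseline:

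| Loss | True difference 3: estimate | Power | No true effect: type I error |
|---|---|---|---|
| None | 3.00 | 0.93 | 0.05 |
| Worst 1, placebo only | 2.77 | 0.89 | 0.063 |
| Worst 3, placebo only | 2.40 | 0.80 | 0.12 |
| Worst 3, temanogrel only | 3.60 | – | 0.12 |
| Worst 3 of the 66, whatever the arm | 2.57 | 0.87 | 0.05 |
| Worst 3 in each arm | 3.00 | – | – |

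Type I error rises only when the loss is one-sided.

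**3. Graded loss.** A less extreme version lets the odds of a missing value rise 2-fold, 3-fold or 7.4-fold per SD of worse outcome.
- 9% missing in one arm, none in the other, no true effect: type I error about 0.056, 0.063 and 0.08.
- 9% against 3%: about 0.053 to 0.062.
- 9% in both arms: 0.05.
- True difference 3, 9% lost on placebo only: estimates of about 2.8, 2.7 and 2.5.

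**4. General formula.** Bias in the difference = fP × DP − fT × DT. Here f is the fraction missing in an arm, and D is how much worse the missing subjects are than the observed ones.
- 3/33 missing in each arm with equal D: zero.
- 5/33 against 1/33 with D = 7 (2 SD): (4/33) × 7 = 0.85.
- 3/33 in each arm with D = 0 on placebo and 7 on temanogrel: (3/33) × 7 = 0.64.

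So a material bias needs either clearly unequal loss or clearly different kinds of missing subject in the two arms.

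**5. What the documents offer on mechanism.** Section 10.9 concerns the timing and order of Day 1 events; it does not say that IMR may be skipped. Section 4.1 requires NSTEMI/UA patients to be hemodynamically stable with TIMI flow grade 2 or 3. Post-PCI physiology is due within 15 minutes of the end of PCI (Section 10.4.1). Treatment is a single blinded dose. Nothing in the text points to loss that differs by arm.

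**The case for a change.** The best argument for a change is that the justification in Section 11.4 does not fit the likeliest cause of loss. Short duration guards against dropout over time, whereas a missed Post-PCI IMR would be a procedural failure on Day 1. Sections 5.1 and 10.3 foresee bail-out therapy for no reflow, so poor flow during the procedure was anticipated. The 9-subject margin protects power and does nothing for bias. Stating the assumption, tabulating missing values by arm and reason, and naming one missing-not-at-random check would cost little.

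Part of this stands. The protocol does not state the assumption, names no such check and gives the mFAS no role. The rest is weaker:
- That bail-out patients would miss the measurement is an inference, and bias also needs them to do so unequally by arm.
- Section 12.5 asks investigators to document and explain deviations, so a reason for a missed measurement should be on record.
- The final report contents attached to the 07 October 2022 Note to File include a disposition table and a listing of each subject's Baseline, Pre-PCI and Post-PCI indices. Missing values can be counted by arm from these.
- Sensitivity analyses were assigned to the SAP. Its draft is not among the documents, so its silence cannot be presumed, and it stayed in draft because the programme was terminated.
- A worst-rank test answers a different question from the mean difference in IMR, and its use here is debatable.

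**Conclusion.** No change follows. Any analyst who fits this ANCOVA without imputation will use the subjects with both IMR values, which is a sound analysis under the plan's expectation of few missing values. Writing down the missing-at-random assumption would make the text clearer and leave the estimate, standard error and p-value as they are.

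The possible harm is bounded but hypothetical. It reaches 0.60 IMR units and a type I error of about 0.12 if exactly the three worst of 33 are lost in one arm. Under graded one-sided loss of 9% it is about 0.2 to 0.5 units and 0.06 to 0.08. Equal fractions lost under the same rule in both arms give essentially none. These figures take the plan's SD of 3.5 and 33 per arm, use assumed loss patterns, and ignore baseline adjustment.

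Section 11.8 calls the study an exploratory proof of concept. After termination, the listed report contents include summaries of coronary physiology and no ANCOVA. The conclusion would be different if the IMR listing showed several missing Post-PCI values concentrated in one arm.
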